### 10.3. Statistical Analyses

#### 10.3.1. General Statistical Considerations

Statistical analysis of this study will be the responsibility of Eli Lilly and Company or its designee.

Geographic regions will include United States (US) and other (Non-US). Unless otherwise specified, the statistical analysis models will adjust for geographic region and prior exposure to biologic therapy use (yes/no).

Any change to the data analysis methods described in the protocol will require an amendment ONLY if it changes a principal feature of the protocol. Any other change to the data analysis methods described in the protocol, and the justification for making the change, will be described in the clinical study report (CSR). Additional exploratory analyses of the data will be conducted as deemed appropriate. Complete details of the planned analyses will be documented in the SAP.

#### **10.3.1.1. General Considerations for Analyses in the Induction Period**

Continuous data will be summarized in terms of the mean, standard deviation, minimum, maximum, median, and number of observations. Categorical data will be summarized as frequency counts and percentages. Comparisons between each LY3074828 dose regimen (30 mg, 100 mg, 300 mg) and placebo will be performed for all analyses in the induction period with no adjustment for multiple comparisons.

For the induction period efficacy, health outcomes, and safety analyses, baseline is defined as the last available value before the initial randomization, which in most cases will be the measure recorded at Week 0 (Visit 2). Change from baseline will be calculated as the visit value of interest minus the baseline value.

Treatment comparisons of categorical efficacy variables will be conducted using a logistic regression analysis with treatment, geographic region (US/Non-US), and prior exposure to biologic therapy use (yes/no) in the model. The proportions and 95% confidence intervals will be reported.

Treatment comparisons of continuous efficacy and health outcome variables will be made using mixed-effects for repeated measures (MMRM).

When MMRM is used, the model includes treatment, geographic region (US/Non-US), prior exposure to biologic therapy use (yes/no), baseline value, visit, and the interaction of treatment-by-visit as fixed factors. The covariance structure to model the within-subject errors will be unstructured. If the unstructured covariance matrix results in a lack of convergence, the heterogeneous Toeplitz covariance structure, followed by the heterogeneous autoregressive covariance structure will be used. The Kenward-Roger method will be used to estimate the denominator degrees of freedom. Type III sums of squares for the least squares means will be used for the statistical comparison; the 95% confidence interval will also be reported. Treatment group comparisons with placebo at Week 16 (Visit 7) and all other visits will be tested.

Fisher's exact test will be used for categorical safety data including AE, baseline, and discontinuations. Continuous vital sign and laboratory values will be analyzed by analysis of covariance (ANCOVA) with treatment and baseline value in the model. Other continuous safety variables will be analyzed by t-tests, unless otherwise stated.

### 10.3.1.2. General Considerations for Analyses in the Maintenance Period

For maintenance period efficacy analysis, unless otherwise stated, baseline is defined as the last available value before the initial randomization in the induction period which in most cases will be the value recorded at Week 0 (Visit 2).

For maintenance period safety analysis, for subjects

- randomized to placebo in the induction period and for subjects who did not achieve PASI 90, baseline is defined as the last available value before the treatment reassignment in the maintenance period (Week 16, Visit 7)
- who did achieve PASI 90, baseline is defined as the last available value before the initial randomization which in most cases will be the measure recorded at Week 0 (Visit 2)

Change from baseline and 95% confidence interval will be calculated by treatment as the visit value of interest minus the baseline value for continuous variables. The proportion and 95% confidence interval will be reported by treatment for categorical variables.

The Kaplan-Meier product limit method will be used to estimate the survival curves for time-to-event variables; median time to loss of response will be summarized by treatment.

### 10.3.1.3. Missing Data Imputation

Analysis of categorical efficacy and health outcome variables will be assessed using a NRI method. Subjects will be considered a nonresponder for the NRI analysis if they do not meet the clinical response criteria or have missing clinical response data at the analysis time point. Randomized subjects without at least 1 postbaseline observation will also be defined as nonresponders for the NRI analysis.

## 10.3.2. Treatment Group Comparability

### 10.3.2.1. Subject Disposition

Subject disposition will be summarized for each treatment period. Reasons for discontinuation from the study will be summarized. Treatment comparisons of reasons for discontinuation during induction will be made using Fisher's exact test.

### 10.3.2.2. Subject Characteristics

Subject characteristics and baseline clinical measures will be summarized for each treatment period. Baseline characteristics will include gender, age, age category, weight, race, geographic region (US/Non-US), baseline disease severity, duration of disease, prior exposure to biologic therapy, previous nonbiologic systemic therapy, and previous biologic therapy. Baseline clinical measurements will include sPGA score, PASI total score, BSA, PSSI, PSS total score, PatGA, DLQI total score, SF-36 (PCS), and SF-36 (MCS).

Treatment group comparisons for induction will be conducted using Fisher's exact test for categorical data and a 1-way analysis of variance (ANOVA) for continuous data.

### 10.3.2.3. Concomitant Therapy

Previous and concomitant medications will be summarized for subjects who enter each treatment period and will be presented by anatomical therapeutic chemical (ATC) drug classes using the latest version of the World Health Organization (WHO) drug dictionary. Treatment group comparisons for induction will be conducted using Fisher's exact test.

### 10.3.2.4. Treatment Compliance

Treatment compliance with investigational product will be summarized for subjects who enter the induction and maintenance periods. A subject will be considered significantly noncompliant if he or she fails to attend for administration of study medication within the required treatment window as defined in the Schedule of Activities (Section 2). Overall compliance with therapy is defined to be missing no more than 20% of the expected doses and not missing 2 consecutive doses. Proportions of subjects who demonstrate overall compliance during the induction period will be compared between treatment groups using Fisher's exact test.

## 10.3.3. Efficacy Analyses

Primary and secondary analyses will be based on the intent-to-treat (ITT) population.

### 10.3.3.1. Primary Analyses

Treatment comparisons between each LY3074828 dose regimen (30 mg, 100 mg, 300 mg) and placebo in the proportion of subjects achieving PASI 90 at Week 16 will be analyzed using logistic regression with NRI as described in Section 10.3.1.1.

### 10.3.3.2. Secondary Analyses

Treatment comparisons between each LY3074828 dose regimen (30 mg, 100 mg, 300 mg) and placebo at Week 16 in the proportion of subjects achieving PASI 100, PASI 75, sPGA 0 (clear), and sPGA 0/1 will be analyzed using logistic regression with NRI as described in Section 10.3.1.1. The proportion and 95% confidence interval of subjects achieving PASI 100, PASI 90, and PASI 75 at Weeks 52, 104, and 120 will be summarized by treatment.

Treatment comparisons between each LY3074828 dose regimen (30 mg, 100 mg, 300 mg) and placebo in the change from baseline to Week 16 in health outcome measures DLQI, SF-36, CCI will be analyzed using the MMRM model as described in Section 10.3.1.1. The change from baseline and 95% confidence interval for health outcome measures DLQI, SF-36, and PatGA at Weeks 52, 104, and 120 will be summarized by treatment.

The Week 120 (Visit 804) data will be summarized by including only subjects who both enter and complete the post-treatment follow-up period of Study AMAF.

CCI

C  
C  
I

[Redacted text block containing multiple lines of blacked-out content]

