### Objective(s)/Endpoints:

Objectives	Endpoints

Primary
 
To test the hypothesis that treatment with LY3074828 is superior to placebo in inducing PASI 90 response at Week 16 in subjects with moderate-to-severe plaque psoriasis
	
The proportion of subjects achieving PASI 90 at Week 16 (NRI)

Secondary
 
 
To evaluate the safety and tolerability of treatment with LY3074828
 
To evaluate the efficacy of treatment with LY3074828 compared to placebo in inducing PASI 100 and PASI 75 at Week 16
 
To evaluate the efficacy of treatment with LY3074828 compared to placebo in inducing sPGA 0 (clear) and sPGA 0/1 at Week 16
 
To evaluate the effect of LY3074828 on patient reported outcome measures: PSS, PatGA, DLQI, and SF-36 at Week 16
 
To characterize the long-term efficacy of LY3074828 on the PASI 100, PASI 90, and PASI 75 responses at Week 52, 104, and 120
 
To characterize the long-term efficacy of LY3074828 on patient reported outcome measures PSS, PatGA, DLQI, and SF-36 at Weeks 52, 104, and 120
 
To characterize the PK of LY3074828
 
	
 
Adverse event and discontinuation rates
 
The proportion of subjects achieving PASI 100 and PASI 75 at Week 16 (NRI)
 
The proportion of subjects achieving sPGA 0 and sPGA 0/1 at Week 16 (NRI)
 
The mean change from baseline for PSS, PatGA, DLQI, and SF-36 at Week 16
 
The proportion of subjects achieving PASI 100, PASI 90, and PASI 75 at Weeks 52, 104, and 120
 
The mean change from baseline for PSS, PatGA, DLQI, and SF-36 at Weeks 52, 104, and 120
 
Clearance and volume of distribution
 

Abbreviations: DLQI = Dermatology Life Quality Index; NRI = nonresponder imputation; PASI = Psoriasis Area and Severity Index; PASI 75 = 75% improvement in PASI from baseline; PASI 90 = 90% improvement in PASI from baseline; PASI 100 = 100% improvement in PASI from baseline; PatGA = Patient Global Assessment; PK = pharmacokinetics; PSS = Psoriasis Symptom Scale; SF-36 = Short-Form Health Survey; sPGA = static Physician's Global Assessment.

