## 8.2. Discontinuation from the Study

Some possible reasons that may lead to permanent discontinuation include:

- enrollment in any other clinical trial involving an investigational product or enrollment in any other type of medical research judged not to be scientifically or medically compatible with this study. **Note:** Enrollment in the separate long-term extension study shall be considered compatible with Study AMAF, provided that the subject is not permanently discontinued from treatment or from the study, and provided that the subject is deemed eligible for enrollment in the separate long-term extension study.
- participation in the study needs to be stopped for medical, safety, regulatory, or other reasons consistent with applicable laws, regulations, and good clinical practice (GCP)
- investigator decision
  - the investigator decides that the subject should be discontinued from the study
  - if the subject, for any reason, requires treatment with another therapeutic agent that has been demonstrated to be effective for treatment of the study indication, discontinuation from the study occurs prior to introduction of the new agent
- subject decision
  - the subject requests to be withdrawn from the study
- AE
  - If the investigator decides that the subject should be withdrawn because of an AE/SAE or a clinically significant laboratory value, the investigational product is to be discontinued and appropriate measures are to be taken. Lilly or its designee is to be alerted immediately. Refer to Safety Evaluations, Sections 9.2 and 9.2.1.
- subject experiences a systemic hypersensitivity event (such as anaphylaxis) following administration of investigational product.
- subject becomes pregnant

Subjects who discontinue the study early will have end-of-study procedures as outlined in Visit 804 in the Schedule of Activities (Section 2).

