### 10.2. Populations for Analyses

For purposes of analysis, the following populations are defined:

Population	Description
Intent-to-treat (ITT)	All randomized subjects, even if the subject does not take the assigned treatment, does not receive the correct treatment, or otherwise does not follow the protocol. Subjects will be analyzed according to the treatment to which they were assigned. Unless otherwise noted, efficacy and health outcomes analyses for the induction period will be conducted on this population.
Safety	All randomized subjects who received at least 1 dose of study treatment. Subjects will be analyzed according to the treatment to which they were assigned. Safety analyses for the induction period will be conducted on this population.
Maintenance period	All ITT subjects who received at least 1 dose of study treatment and have entered the maintenance period at Week 16 (Visit 7). Efficacy, health outcomes, and safety analyses for the maintenance period will be conducted on this population.
Follow-up	All ITT subjects who received at least 1 dose of study treatment and have entered the post-treatment follow-up period. Subjects will be analyzed according to the last treatment they received before entering the post-treatment follow-up period. Efficacy, health outcomes, and safety analyses for the post-treatment follow-up period will be conducted on this population.

Abbreviation: ITT = intent-to-treat.

Additional analysis populations will be described in the statistical analysis plan (SAP) as deemed appropriate.

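### The Week 120 PASI summary keeps only follow-up completers, against the plan's own population and missing-data rules, and is likely to overstate response

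*Protocol*

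**What the plan says.** The Protocol Synopsis lists as a secondary endpoint "The proportion of subjects achieving PASI 100, PASI 90, and PASI 75 at Weeks 52, 104, and 120". Protocol Section 10.3.3.2 makes the analysis descriptive: the proportions and 95% confidence intervals "at Weeks 52, 104, and 120 will be summarized by treatment". The same section then sets the Week 120 (Visit 804) analysis set by "including only subjects who both enter and complete the post-treatment follow-up period of Study AMAF".

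Other parts of the plan point elsewhere:

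- Protocol Section 10.2 defines the Follow-up population as "All ITT subjects who received at least 1 dose of study treatment and have entered the post-treatment follow-up period", and adds: "Efficacy, health outcomes, and safety analyses for the post-treatment follow-up period will be conducted on this population". It sets no completion condition.
- Protocol Section 10.3.1.3 treats subjects as nonresponders for categorical efficacy variables if they "have missing clinical response data at the analysis time point". The visible text does not limit this rule to one study period.
- Protocol Section 10.3.3 bases secondary analyses on the ITT population.
- SAP Section 6.1.2.1 counts everyone with Visit 29 as having entered follow-up, and SAP Section 6.3.1 keeps NRI. SAP Table 6.3 has no follow-up or Week 120 row, although SAP Section 4.2 repeats the Week 120 objective.

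**The concern.** The follow-up schedule (Protocol Section 2) contains no dosing row, so psoriasis may return during these 16 weeks. Under Protocol Section 8.2, when a subject requires another agent shown to be effective in psoriasis, "discontinuation from the study occurs prior to introduction of the new agent". A relapse that needs such treatment therefore takes the subject out of the study, and the completer rule then takes the subject out of the Week 120 denominator. Whether a subject is counted can depend on the outcome being counted.

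At stake is the Week 120 statement on PASI 75, 90 and 100. No test is attached to it, so the proportion and its interval are the whole result. If the denominator is selected on outcome, nothing else visible in the plan corrects the impression.

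**Working it through.** **Is there a stated figure to reproduce?** Not for Week 120: the documents show neither a follow-up dropout rate nor a Week 120 response rate. The plan's only visible power figure (over 99% at Week 16, SAP Section 5.2) does not bear on this point.

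**Step 1: which subjects each rule counts**

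| Rule | Left follow-up early, no Week 120 value |
|---|---|
| Section 10.3.3.2 (completers) | not in the denominator |
| Section 10.2 (all who entered) | in the denominator |
| Section 10.3.1.3 (NRI) | in the denominator as a nonresponder |

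The first row cannot be reconciled with the other two.

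**Step 2: gap to the plan's own NRI rate.** Set transfers to the extension study aside. Let E be the number who entered, L the number who left before Week 120, r the responders among completers, and d = L/E.

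- Completer rate c = r/(E − L)
- NRI rate in entrants = r/E = c × (1 − d)
- Gap = c × d

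The gap is never negative. It is positive as soon as one subject leaves and one completer responds. With assumed values of c and d, the table gives the NRI rate, with the gap in percentage points in brackets:

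| c | d = 5% | d = 10% | d = 20% | d = 30% |
|---|---|---|---|---|
| 40% | 38.0% (2) | 36.0% (4) | 32.0% (8) | 28.0% (12) |
| 50% | 47.5% (2.5) | 45.0% (5) | 40.0% (10) | 35.0% (15) |
| 60% | 57.0% (3) | 54.0% (6) | 48.0% (12) | 42.0% (18) |

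In counts, again by assumption: 40 enter and 18 complete as responders.

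- All entrants with NRI: 18/40 = 45.0% (Wilson 95% CI 30.7 to 60.2).
- Completers only: 18/36 = 50.0% if 4 leave, 18/32 = 56.3% if 8 leave, and 18/28 = 64.3% if 12 leave.

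**Step 3: gap to the true rate among entrants.** If leavers would respond at rate q, the true rate is c(1 − d) + qd, and the completer rate is off by d × (c − q). With c = 50% and d = 20%:

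| q | Completer rate minus true rate |
|---|---|
| 0% | +10 points |
| 25% | +5 points |
| 50% | 0 |
| 100% | −10 points |

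The bias is upward only when q is below c. Section 8.2 makes that likely for subjects who leave because of relapse.

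**Step 4: who else leaves, and what Visit 804 is.** Footnote a to the follow-up schedule describes subjects who want to join the extension, cannot yet do so, and stay in follow-up until eligible. They then leave with the V804/ET assessments. Visit 804 is thus both the Week 120 visit and the early-termination visit. Section 8.2 also applies its procedures to anyone who discontinues the study early.

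**The case against.** The strongest defence is that the word for completion does useful work. Because Visit 804 also serves as the early-termination visit, requiring completion keeps assessments made at other times from being reported as Week 120. This stands: striking the requirement without a visit rule would lose that protection. A tempting remedy is to strike it and apply NRI to everyone who leaves. The documents do not support that, because subjects who move to the extension from follow-up would be scored as failures even if their skin is clear.

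A reader might also infer that the reported rate is certainly inflated because relapsers are removed. The documents do not show this. Section 8.2 offers relapse needing a new agent as one of several possible reasons for leaving. The table of permitted psoriasis medication (Table AMAF.4) is blacked out, so it is unclear how often relapse would force an exit. Step 3 shows that the bias vanishes if leavers respond as often as completers, and reverses if they respond more often.

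Other mitigating points hold in part:

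- SAP Section 6.5 lists discontinuations in follow-up, with reasons where known, so attrition would be visible.
- Text after the disputed sentence is blacked out, so a supplementary analysis cannot be excluded.
- The SAP (28 June 2017) predates both protocol amendments and contains no extension text.
- Subjects who roll over at Week 104 have no AMAF Week 120 visit, so the Week 120 group is self-selected under either denominator.

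None of this reconciles Section 10.3.3.2 with Sections 10.2 and 10.3.1.3. The requirement to enter follow-up already removes the Week 104 rollovers. The completion requirement additionally removes everyone who leaves later, whatever the reason.

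**Conclusion.** The point holds as an internal contradiction with a likely upward bias. Against the plan's own NRI rule the direction is arithmetic: the completer rate is higher by c × d, or 2 to 18 points for completer rates of 40-60% and dropout of 5-30%. Both ranges are assumptions, and the true size cannot be known from the documents. Against the true rate among entrants, overstatement further requires that leavers respond less often than completers. Section 8.2 makes this plausible but does not guarantee it.

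The reach is limited. Week 120 is descriptive, so no test, significance level or power is affected, and the Week 16 primary analysis is untouched. Correcting the denominator would also not give a rate for all treated subjects, since those who roll over to the extension at Week 104 remain outside it. The change is worth making, but it does not threaten the trial's main conclusion.

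**What to change.** Reconcile Protocol Sections 10.2, 10.3.1.3, 10.3.3 and 10.3.3.2 as follows:

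1. Summarise Week 120 PASI 75, 90 and 100 in all subjects who entered AMAF follow-up, which excludes those who rolled over to the extension at Week 104.
2. Apply NRI to those who leave before Week 120 for any reason other than transfer to the extension.
3. State a separate rule for subjects who transfer to the extension from follow-up, and do not score them as nonresponders.
4. State that V804/ET assessments made early are not Week 120 observations.
5. Keep the completer figure as supportive, with counts and reasons for leaving by treatment.
6. Add a Week 120 row to SAP Table 6.3, and align the follow-up entry definition in SAP Section 6.1.2.1, which now counts everyone with Visit 29.

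The cost is a few sentences across the two documents, one extra table and a somewhat lower reported Week 120 rate. No new data need to be collected: PASI is already scheduled at every follow-up visit, and reasons for discontinuation are already to be reported.

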**10.3.4. Safety Analyses**

Safety will be assessed by evaluating AE, laboratory analytes, vital signs, ECGs, and C-SSRS.

The induction period safety analyses will compare LY3074828 to placebo for which treatment group comparisons will be analyzed using the methods described in Section 10.3.1.1. The maintenance period safety analyses will summarize safety measures by treatment. Summaries of safety data collected during the follow-up period will be presented separately.

AEs will be coded according to the *Medical Dictionary for Regulatory Activities* and summarized by system organ class, preferred term, severity, and relationship to investigational product. A treatment-emergent adverse event (TEAE) is defined as an event that first occurred or worsened in severity after baseline. For each event classification term, the number of subjects experiencing a TEAE with that classification term will be tabulated.

Treatment-related TEAEs are defined as events that are indicated by the investigator on the eCRF to be related to treatment. If a subject reports the occurrence of a particular event more than once, the most severe of those events will be included in the summary tables of TEAEs, and the most severe of the most related of those events will be included in the summary tables of

treatment-related events. For events that are gender specific, the denominator and computation of the percentage will only include subjects from the given gender.

Additional safety parameters include laboratory analytes, vital signs, ECGs, and C-SSRS. Laboratory analytes and vital signs will be presented as mean changes from baseline and as incidence of abnormal values. ECG and C-SSRS data will be listed by subject. Other covariate data, including body weight, will be summarized by treatment group.

